1

Research protocol

4th National Registry of Cardiovascular Surgery (CCV) in Argentina

-Version N ° 3- 8 of JULY 2021

Page 2

2

Confidentiality notice: The concepts and information included in this document are confidential and exclusive and not they must be disclosed in whole or in part without the express written consent of the coordinator.

Page 3

3

PROTOCOL SUMMARY

> Title

1- Prospective registry of patients undergoing CCV in Argentina

> Study Phase

1- Prospective Registry (IV)

> Evaluation

1- Follow-up of patients during hospitalization and 30 days after surgery.

> Primary Objectives

^{1.a.}

Determine the evolution and surgical complications in patients undergoing CCV

^{1.b.}

To determine the association between different risk variables during the intranosocomial stay and at 30 days of discharge including nosocomial readmission during the 30-day follow-up.

> Secondary Objectives

To determine the association between different variables that occurred before, during and after the surgical intervention.

To determine the association between different variables of risk at discharge and the rate of complications, including

mortality and readmissions during the 30 days following discharge, such as:

Cardiovascular mortality, all-cause mortality, rehospitalization, infectious complications.

To determine the association between different variables with cardiovascular mortality in relation to CCV.

Assess eventual complications 30 days after hospital discharge

Page 4

4

> Study Design

National, multicenter, analytical, prospective cohort study for prognostic evaluation in patients undergoing cardiovascular surgery (CCV)

> Sample Size

The largest number of patients (between 2000 and 3000) will be enrolled during a set period of time (1 year), from

October 1, 2020 to September 30, 2021

> Eligibility Criteria

Over 18 years

Myocardial revascularization surgery

Valvular surgeries

Ascending Aortic Surgery

Type A Aortic Dissection Surgery

Combined surgery

➤ **Exclusion Criteria**

Cardiovascular surgery for congenital pathologies

Peripheral vascular surgery

Cardiovascular surgery secondary to trauma

Thoracic and abdominal aorta pathology

Other surgeries

➤ **Procedures**

Various centers are included nationwide with a CCV service capable of admitting and intervening patients with criteria already established.

They are arranged below:

Leben Health

Private Hospital Santa Clara de Asis

[name] Hospital

Pasteur Clinic

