Atrioventricular block Yes No
Complex ventricular arrhythmia Yes No
Transient pacemaker Yes No
Permanent pacemaker Yes No
I do prophylaxis for postoperative AF Yes No
Drug used

POP day of initiation of prophylaxis for AF

Renal failure Yes No
(Increase in creatinine above 50%
with respect to the baseline value and / or

17

hemodialysis)

Hemodialysis Yes No

Stroke Yes No

(Focal and / or diffuse brain injury confirmed by clinical findings and / or computed tomography with sensory or motor sequelae upon discharge of the patient)

Transient ischemic accident Yes No

Psychiatric disorders Yes No

(Any of the following: delirium, hallucinations, psychomotor arousal)

Required treatment with ... Risperidone

Quetiapine

Haloperidol

Other

Respiratory distress syndrome Yes No

(Infiltrate in 4 quadrants - PCP <18 - PAFI <200)

Fever without obvious focus Yes No

Sepsis Yes No

(Suspected or documented infection with dysfunction of target organ and at least two of the following criteria: Temperature > 38 ° C or <36 ° C, White blood cell count greater than 12,000 uL or less at 4000 uL, Tachycardia, Tachypnea > 30 rpm, Altered mental state, Positive culture of primary focus of infection, mean arterial pressure less than 70 mm Hg for a minimum fingers

hours, poor distal perfusion ("))

Urinary infection Yes No

Respiratory infection Yes No

Surgical wound infection Yes No

Superficial wound infection Yes No

Saphenous wound infection Yes No

Sternal infection Yes No

Mediastinitis Yes No

Sternal reopening requirement Yes No

Sternal reopening POP day

Sternal mechanical instability Yes No

COVID-19 infection development during internment

18

If not

TOTAL days of hospitalization until discharge

POSTOPERATIVE days until discharge

Discharge

Alive

Dead _____

Death cause:

Infectious

Cardiovascular

Distributive shock

Hemorrhage

Cardiac tamponade

Stroke

Respiratory distress

Multi-organ failure

Another cause

Death from infectious cause: Mediastinitis Pneumopathy Sepsis Other

Identified germ

Death from cardiovascular cause: Myocardial infarction Arrhythmia Heart failure

Pre Registration Laboratory

Hematocrit _____ Blood glucose _____

Uremia _____ Creatinine _____

Medication at discharge ASA

Clopidogrel

Ticagrelor

Prasugrel

Statins

Beta-blockers

Sartan

ACE inhibitors

Loop diuretic

Thiazide

Spironolactone

Insulin

Oral hypoglycemic

Anticoagulants

Investigator Notes

19

Follow-up

Re-internment Yes No

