(Within the first 30 days after discharge)

Cause of re-admission:

Heart failure

Respiratory insufficiency

Renal insufficiency

Sepsis:

Other

Sepsis Yes: Sepsis starting point: Mediastinitis or other focus

Another cause of re-admission

Death no

Death Yes:

(Within the first 30 days after discharge)

Cause of death in follow-up: Cardiovascular- NON-cardiovascular cause

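### The follow-up form codes infection only as a septic re-admission, so infectious complications after discharge are under-captured and cannot be compared with the in-hospital items

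*Protocol*

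**What the plan says.** **Outcome.** In the Protocol Summary, under Secondary Objectives, the outcomes for the 30 days after discharge include "Cardiovascular mortality, all-cause mortality, rehospitalization, infectious complications".

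**Hospital stage.** In the Postoperative part of the form, sepsis is a Yes/No item with a written definition that begins "Suspected or documented infection with dysfunction of target organ and at least two of the following criteria". Mediastinitis is its own item, "Mediastinitis Yes No". Urinary, respiratory, surgical wound, superficial wound, saphenous wound and sternal infection are also separate Yes/No items. None of them is tied to sepsis.

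**Follow-up stage.** The Follow-up part lists the causes of re-admission as heart failure, respiratory insufficiency, renal insufficiency, sepsis and other, with a further line for another cause. The only infectious detail is "Sepsis Yes: Sepsis starting point: Mediastinitis or other focus".

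**The concern.** The same infection is recorded differently before and after discharge. In hospital, a mediastinitis is counted whether or not the patient is septic. After discharge, it has a code only if it is the focus of a septic re-admission. The other infections that have their own hospital items have no named field at follow-up at all.

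What is at stake is a named outcome. Primary objective 1.b includes re-admission within 30 days, and the secondary objectives relate risk variables at discharge to infectious complications in that period. If the coded fields miss infections that do not meet the sepsis definition, the 30-day infection count is too low. An association estimated from it then concerns only the septic cases. An analysis plan cannot restore a code that the form did not collect.

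**Working it through.** The protocol gives no figure on this point, so there is none to reproduce. The check is to follow one type of patient through the form.

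| Event | Hospital stage (Postoperative) | After discharge (Follow-up) |
|---|---|---|
| Mediastinitis with sepsis | Mediastinitis Yes; sepsis Yes | Sepsis, with mediastinitis as starting point |
| Mediastinitis without organ dysfunction | Mediastinitis Yes; sepsis No | Residual cause only; no mediastinitis code |
| Wound, sternal, respiratory or urinary infection with sepsis | Own item Yes; sepsis Yes | Sepsis, with another focus; the site is not named |
| The same infections without organ dysfunction | Own item Yes; sepsis No | Residual cause only; no infection code |

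1. The sepsis definition requires infection, target-organ dysfunction and at least two listed criteria. An infection without organ dysfunction fails it.
2. The definition appears once, in the section headed Specific Protocol (Operational Definition of Variables). The follow-up form uses the same word and gives no other rule, so the natural reading is that the definition carries over.
3. On that reading, rows 2 and 4 cannot be entered as sepsis at follow-up. They can go only under the residual cause.
4. The follow-up death field does not help. It offers only "Cause of death in follow-up: Cardiovascular- NON-cardiovascular cause", which does not identify infection.
5. If a site instead enters a non-septic infection as sepsis, it departs from the only definition given. Every sepsis entry is still an infection, however, so on either reading the coded sepsis count is at most the number of re-admissions for infection.

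The direction is therefore known: the coded fields give a minimum for infectious re-admissions. How far they fall short depends on the share of infectious re-admissions that do not meet the sepsis definition, which the protocol does not give. It gives only an enrolment range of 2000 to 3000 patients.

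This check concerns patients who are re-admitted. Infections treated without re-admission are a separate matter.

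**The case against.** The strongest reply is that the form does not force a wrong entry. A non-septic mediastinitis can be placed correctly under the residual cause, and the line for another cause lets the site describe it. Using that description or the source record, the event can be recoded and a total over both stages formed for re-admitted patients. This stands as far as it goes. The information is not lost beyond recovery, and it would be wrong to say that a total mediastinitis rate cannot be obtained. What remains is that the coded fields do not provide it, and that capture depends on what each site wrote.

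A reader might also infer more than the protocol supports:

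- **That septic re-admissions are counted under different rules in the two stages.** Re-admission is recorded only at follow-up, so there is no second stage to conflict with.
- **That two sepsis definitions are in force.** Only one is printed. At most, it is not repeated at follow-up.
- **That the hospital death list adds a third conflicting rule.** It reads "Death from infectious cause: Mediastinitis Pneumopathy Sepsis Other". It answers a different question, and it would conflict only if a single choice were required, which is not stated.
- **That predictors of sepsis will be estimated on events pooled over both stages.** The protocol states no such analysis.

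Finally, Version 3 is dated 8 July 2021 and enrolment ends on 30 September 2021, so new boxes come late. That is fair and limits what a form change alone can do. It is why recoding is part of the fix.

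**Conclusion.** The point holds in this form: infectious complications are a named outcome after discharge, but the follow-up form codes infection only through septic re-admission. Re-admissions for mediastinitis or another infection without organ dysfunction have no infection code. The coded post-discharge infections are under-captured and are not comparable with the in-hospital items.

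This rests on one assumption, that the hospital sepsis definition applies at follow-up. If it does not, sepsis is undefined there and sites may differ, which does not make the two stages comparable either.

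No size can be stated. It is tempting to give a ratio of broad to strict sepsis re-admissions. If 30% to 50% of infectious re-admissions were septic, the ratio would be 1/0.5 = 2 to 1/0.3 = 3.3. That is only the assumed share turned upside down, and it supposes that every infectious re-admission is entered as sepsis. It is not evidence from this registry.

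The form should be changed: a named outcome is affected and the change is small.

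**What to change.** **Form.** On the follow-up page, add infection as a cause of re-admission, with the sub-items already used in hospital: mediastinitis, sternal, surgical, superficial and saphenous wound, respiratory and urinary, plus other. At the least, add a mediastinitis Yes/No. Keep sepsis as a separate Yes/No, and state that the definition in the Postoperative part applies.

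**Patients already followed.** Recode the re-admissions entered as sepsis or as other, using the recorded cause or the source record.

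**Reporting until recoding is complete.** Describe the post-discharge result as re-admission for infection, say that it is a minimum from the coded fields, and do not compare coded mediastinitis between the hospital and follow-up stages.

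**Cost.** A few tick boxes and some recoding by sites, with no new visits or patients. New boxes reach only patients not yet followed up. From the version date to the end of enrolment, counting both days, there are 24 + 31 + 30 = 85 of 365 days, about 23% of the enrolment period, plus those enrolled earlier whose 30 days have not ended. For the rest, the result depends on how fully the cause of re-admission was recorded.
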